3.1.2. Secondary Objectives

The original key secondary objectives are to assess simufilam's effect on changes from baseline to week 76 in the iADRS, NPI-10, MMSE, CDR-SB, and the ZBI. These are the secondary objectives for which multiplicity will be controlled. The early termination of the study did not change any of the secondary objectives.

Additional secondary objectives are to compare the co-primary and secondary endpoints in the subgroup of mild AD patients (stage 4 AD) with baseline MMSE scores of 21-27.

Additional secondary objectives that are not multiplicity controlled include the following:

- Mean change in the ADAS-Cog12 from baseline to Weeks 4, 16, 28, 40, 52, and 64
- Mean change in ADCS-ADL from baseline to Weeks 4, 16, 28, 40, 52, and 64.
- Mean change in the iADRS (range 0 139, lower score indicates greater impairment) from baseline to Weeks 4, 16, 28, 40, 52, and 64.
- Mean change in the NPI-10 (range 0 120, higher score indicates greater impairment) from baseline to Weeks 28 and 52
- Mean change in the MMSE (range 0-30, lower score indicates greater impairment) from the screening visit to Weeks 28 and 52.
- Mean change in the ZBI (range 0 88, higher score indicates greater caregiver burden) from baseline to Weeks 4, 16, 28, 40, 52 and 64.

3.1.3. Tertiary Objectives

[figure not shown]
To investigate the effect of simufilam treatment on mean changes from baseline in exploratory CSF, imaging, and plasma biomarkers.

3.2. Estimands

The primary estimand for the primary efficacy endpoints is defined as follows:

Population	The original population was specified as: Participants with mild-to-moderate AD dementia who meet the study's inclusion and exclusion criteria. The
	population of interest was changed after early termination, but while still

Version 1.0 | 28-Feb-2025 Page 15 of 56

	blinded, to: Participants with mild-to-moderate AD dementia who meet the study's inclusion and exclusion criteria, and who have baseline P-tau181 ≥ 44 pg/ml or other evidence of amyloid pathology.
Treatments	Simufilam 100 mg twice daily or placebo (50mg twice daily is secondary).
Endpoints	ADAS-Cog12 (range $0-80$, higher score indicates greater impairment) and ADCS-ADL (range $0-78$, lower score indicates greater impairment).
Summary Measure	Difference between treatments in least squares (LS) mean change from baseline to Week 76.
Intercurrent Events	All deviations from the intended dosing regimens and use of concomitant medication will be handled using a treatment policy strategy. Early study discontinuation will be consistently accounted for using a hypothetical strategy to estimate what would have been observed if the participant had not discontinued.

The estimands for the multiplicity controlled secondary efficacy endpoint(s) are similar to the co-primary estimands. Each secondary estimand has the following components:

Population	The original population was specified as: Participants with mild-to-moderate AD dementia who meet the study's inclusion and exclusion criteria. The population of interest was changed after the early termination, but while still blinded, to: Participants with mild-to-moderate AD dementia who meet the study's inclusion and exclusion criteria, and who have baseline P-tau181 ≥ 44 pg/ml or other evidence of amyloid pathology.
Treatments	Simufilam 100 mg twice daily or placebo (50 mg twice daily is secondary)
Endpoints	iADRS, NPI-10, MMSE, CDR-SB, ZBI
Summary Measure	Difference between treatments in LS mean change from baseline to week 76
Intercurrent Events	All deviations from the intended dosing regimens and use of concomitant events medications will be handled using a treatment policy strategy. Early study discontinuation will be consistently accounted for using a hypothetical strategy to estimate what would have been observed if the participant had not discontinued.

In addition, secondary estimands include the primary and secondary endpoints assessed in the population of participants with stage 4 AD. Stage 4 (mild) is defined as participants with baseline MMSE 21-27. Stage 4 and 5 represent all randomized participants.

3.2.1. Safety Endpoints

The safety endpoints of this study include the following:

• Incidence of adverse events (AEs) including treatment-emergent, serious, related to study

Version 1.0 | 28-Feb-2025 Page 16 of 56

drug, and leading to withdrawal along with AEs by severity and relationship to study drug

- Mean change in clinical laboratory values from baseline to Weeks 4, 16, 28, 40, 52, 64 and 76. Shifts in the normality of clinical laboratory values from baseline to Weeks 4, 16, 28, 40, 52, 64 and 76.
- Mean change in vital signs (blood pressure [supine], temperature, pulse rate) from baseline to Weeks 4, 16, 28, 40, 52, 64 and 76.
- Mean change in body weight from baseline to Weeks 4, 16, 28, 40, 52, 64 and 76.
- Shifts in physical exam (PE) findings from baseline to Weeks 4, 16, 28, 40, 52, 64 and 76.
- Shifts in neurological exam (NE) findings from baseline to Weeks 4, 16, 28, 40, 52, 64 and 76.
- Mean change in ECG parameters from baseline to Weeks 4, 40 and 76.
- Concomitant medications/treatments usage
- Shifts in the C-SSRS from baseline to Weeks 4, 16, 28, 40, 52, 64 and 76.

3.2.2. Pharmacokinetic Variable(s)

Plasma pharmacokinetic (PK) exposure response is part of a sub-study. A visit wise listing of Pharmacokinetic results will be provided. Summary will be presented in a separate report that will be appended to the CSR.

4. Statistical Analysis and Reporting

This SAP addresses the safety and efficacy objectives of the study and describes the statistical methods that Premier Research International LLC and Pentara Corporation will use to analyze the clinical data after the database has been finalized and locked.

[figure not shown]
4.1. Chain of Custody for Clinical Efficacy Data

Study sites collect clinical efficacy data from study participants using an electronic clinical outcome assessment (eCOA) device managed by Signant Health, an independent, outside data management and rater training vendor. Upon receipt of the data, Signant Health's clinical team conducts quality reviews of eCOA endpoints and provides feedback to study raters as appropriate. Signant Health also maintains the clinical efficacy database and transmits it periodically throughout the study to Premier Research to reconcile and package with additional data collected via electronic data capture (EDC). Premier Research also conducts quality reviews and may issue queries to study sites to reconcile any discrepancies. Upon completion of the study and once all visits have been deemed source data verified (SDV), Premier Research will analyze all study data related to safety and directly transmit study data to Pentara Corporation for analysis of all efficacy data. The pre-specified efficacy outcomes for this SAP will be executed by Pentara Corporation (an outside, independent biostatistical consulting firm headed by [name]).

4.2. Introduction

Data processing, tabulation of descriptive statistics, calculation of inferential statistics, and

Version 1.0 | 28-Feb-2025 Page 17 of 56

graphical representations will use SAS (release 9.4 or higher). If the use of other software is required, the final clinical study report will specify the software that was used.

In general, summaries will be provided by study treatment group, unless otherwise noted. The column headings for the summaries will include the randomized treatment groups (Placebo BID, Simufilam 50 mg BID, Simufilam 100 mg BID), unless otherwise noted.

Continuous (quantitative) variable summaries will include the number of participants with non-missing values (n), mean, 2-sided 95% confidence interval (CI), standard deviation (SD) and/or standard error (SE) if applicable, median, and minimum and maximum values.

Categorical (qualitative) variable summaries will include the frequency and percentage of participants who are in the category for each possible value. In general, the denominator for the percentage calculation will be based upon the total number of participants in the study population for the treatment groups (or cohorts) unless otherwise specified.

The minimum and maximum will be reported with the same degree of precision (i.e., the same number of decimal places) as the observed data. Measures of location (mean and median) and bounds of CIs will be reported to 1 degree of precision more than the observed data and measures of spread (SD and SE) will be reported to 2 degrees of precision more than the observed data. Percentages will be presented to 1 decimal place.

Statistical testing and inference methods for safety and efficacy analyses are described below. Efficacy results will be considered statistically significant after consideration of the strategy for controlling the Type 1 error as described in Section 6.1.2 of this SAP. Nominal p-values may be computed for other efficacy analyses as a measure of the association between the endpoint and the treatment effect rather than formal tests of hypotheses. Unless otherwise stated, all statistical tests will be conducted at the alpha = 0.05 (two-sided) level, and a difference resulting in a p- value of ≤ 0.05 will be considered statistically significant. Corresponding 95% two-sided CIs will be presented for statistical tests.

All statistical comparisons will be based on LS means from the relevant contrasts in the mixed model for repeated measurements (MMRM) or analysis of covariance (ANCOVA).

The data from nominal/scheduled protocol clinic visits will be included in visit-based summary tables. Unscheduled assessments, if they occur, and the ET visit data will be mapped to scheduled assessments according to the visit windows defined in section 6.1.5 for all safety and efficacy analyses. See Section 6.1.4 and 6.1.5 of this SAP for more details.

4.3. Interim Analysis and Data Monitoring

No interim efficacy analyses or sample size re-estimations were planned to be conducted.

An external DSMB will be involved in the management of this study. The DSMB meeting will be held periodically for the duration of the study. The purpose of the DSMB is to review the progress of the study with special regard to safety and make recommendations to the Sponsor on how to handle any safety concerns that arise. Further details regarding the DSMB can be found in the DSMB charter which was finalized before the first meeting was scheduled.

Version 1.0 | 28-Feb-2025 Page 18 of 56

Statistical Analysis Plan, Sponsor: Cassava Sciences, Inc. Protocol Number: PTI-125-06 PCN Number: CASA215435

5. Analysis Populations

The following analysis sets were originally planned for this study:

- Intent-To-Treat (ITT) Analysis Set: The ITT analysis set includes all randomized participants.
- Intent-To-Treat mild (ITT-mild) Analysis Set: The ITT-mild analysis set includes all randomized participants who have a baseline MMSE of 21-27.
- Safety Analysis Set (SAF): The SAF analysis set includes all participants who received at least one dose of study treatment. All safety analyses will be completed in the SAF analysis set and participants will be included in the group based on the treatment received.
- **PK sub-study Analysis Set:** The PK sub-study analysis set includes all participants who sign the PK consent and/or re-consent form and have at least one non-missing post baseline PK assessment available.
- **Sub-study analysis sets:** Analysis sets for the Plasma, CSF, and imaging biomarkers will each be created as subsets of the ITT dataset that includes only those participants from the ITT analysis set who were in the relevant sub-studies.
- MRI sub-study Analysis Set: The MRI sub-study analysis set includes all participants who sign the MRI consent and/or re-consent form and have at least one non-missing post baseline MRI assessment available.

After the early termination, the following analysis sets were added:

- Modified intent-to-treat analysis set (mITT): The mITT analysis set is a subset of the ITT analysis set that includes all randomized participants with baseline P-tau181 ≥44 pg/ml or other evidence of amyloid pathology (e.g., Amyloid PET).
- Censored ITT analysis set (cITT): Is the ITT analysis set with observations on and after the November 25, 2024, early termination announcement. Censored observations will be considered missing data.

Assignment of participants to analysis sets will be confirmed at a blinded data review meeting to be held before the study database is locked.

[figure not shown]
6. General Issues for Statistical Analysis

6.1. Statistical Definitions and Algorithms

6.1.1. Baseline

The last observation recorded on or before the first dose of treatment will be used as the baseline observation for all calculations of change from baseline. In most cases, this will be the baseline visit (Day 1) pre-dose observation. In some cases, however, the baseline values may be obtained from the 60-day screening phase. For example, because MMSE is taken at screening but not at the baseline visit, the MMSE value obtained at screening will be used as the baseline value.

Version 1.0 | 28-Feb-2025 Page 19 of 56

6.1.2. Adjustments for Covariates

Primary efficacy analyses will include as covariates the baseline value of the endpoint being analyzed and the MMSE baseline score, along with the interaction of these covariates with Visit. Investigative site (pooled, see section 6.1.6) will also be included as a categorical fixed effect. Covariates observed to be important in post-hoc analyses of the PTI-125-07 study will also be included in sensitivity analyses. See section 8.4 for further details.

6.1.3. Multiple Comparisons

The co-primary endpoints of ADAS-Cog12, and ADCS-ADL in the 100mg treatment arm will each be tested at p=0.05 using the mITT analysis set. Multiplicity among secondary endpoints for the 100 mg arm in the mITT analysis set will be controlled using a hierarchical, gatekeeping strategy. Secondary endpoints in the 100mg arm will be tested in the following order: iADRS, CDR-SB, ZBI, MMSE, and NPI-10. Testing will proceed in this order until the first non-significant p value (p > 0.05). The first endpoint with p > 0.05 and all subsequent endpoints in the order will be declared non-significant, and all endpoints preceding the first non-significant test will be declared significant. Endpoints that were significant in the 100mg arm will also be tested in the 50mg arm at P = 0.05.

For the set of significant endpoints in the 100 mg arm of the mITT analysis set, the corresponding endpoints in the mild subgroup (ITT-mild analysis set) will be tested. Testing for the mild cohort will proceed in the same order as for the secondary endpoints referenced above until the first non-significant p value. The first endpoint with p > 0.05 and all subsequent endpoints in the order will be declared non-significant, and all endpoints preceding the first non-significant test will be declared significant.

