#### 11.3. STATISTICAL ANALYSIS

# 11.3.1. Primary Efficacy Analysis

Each of the two co-primary endpoints will be analyzed using a linear mixed model for repeated measurements. The dependent variable is the change from baseline and the model will include fixed effects for treatment group (three levels), week (7 levels, corresponding to Weeks 4, 16, 28, 40, 52, 64 and 76), the treatment group-by-week interaction, and the randomization stratification variable. The baseline value of the corresponding endpoint will be included as a covariate and the unstructured covariance model will be used. The Baseline Visit (Study Day 1) ADAS-Cog12 and ADCS-ADL assessments will represent the baseline value for these variables.

For each of the two co-primary endpoints, the primary analysis will compare the 100 mg group and the placebo group at Week 76 using a two-sided test at the alpha = 0.05 level of significance. Study success requires that both co-primary comparisons are statistically significant.

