# 11.3.2 Key Secondary Analysis

If both primary comparisons are statistically significant, then the corresponding comparisons at Week 76 for the 50 mg group versus the placebo group will be tested at the alpha = 0.05 level of significance (two-sided).

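### SAP 6.1.3 does not make entry to the 100 mg secondary chain conditional on both co-primaries, so strong 5% familywise control is not secured

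*SAP*

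**What the plan says.** SAP 6.1.3 deals with the co-primaries in one sentence: "The co-primary endpoints of ADAS-Cog12, and ADCS-ADL in the 100mg treatment arm will each be tested at p=0.05 using the mITT analysis set". It then turns to the secondaries: "Multiplicity among secondary endpoints for the 100 mg arm in the mITT analysis set will be controlled using a hierarchical, gatekeeping strategy". The order starts at iADRS ("Secondary endpoints in the 100mg arm will be tested in the following order: iADRS, CDR-SB, ZBI, MMSE, and NPI-10"), testing stops at the first p-value above 0.05, and every endpoint ahead of that failure counts as significant. For the lower dose: "Endpoints that were significant in the 100mg arm will also be tested in the 50mg arm at P = 0.05".

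The protocol is firmer about the co-primaries. Section 11.3.1 says: "Study success requires that both co-primary comparisons are statistically significant". Section 11.3.2 opens the lower dose only on that result: "If both primary comparisons are statistically significant, then the corresponding comparisons at Week 76 for the 50 mg group". Section 11.3.3 leaves the other secondaries at two-sided 0.05 without adjustment.

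Elsewhere in the SAP, 3.1.2 names the five secondaries as multiplicity controlled but gives no rule. Section 4.2 refers the reader to 6.1.2 for the Type 1 error strategy, but 6.1.2 is about covariates. Sections 8.1 and 8.2 say nothing on the order of testing.

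**The concern.** The hierarchy is limited to the secondary endpoints. Neither co-primary is a link in it, and no sentence closes it when a co-primary fails. The protocol cannot supply the missing condition: 11.3.2 covers only the 50 mg co-primary comparisons, and 11.3.3 planned no control for the other secondaries.

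A programmer working from 6.1.3 would therefore test iADRS at 0.05 whatever the co-primaries show. SAP 6.1.7 builds iADRS from ADAS-Cog12 and the instrumental ADL items, so a drug that affects cognition alone can carry it while ADCS-ADL fails. Two things are at stake:

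- The co-primary pair and the chain are two unlinked 5% routes to a claim.
- A trial that fails its own success rule could still report secondary results labelled as multiplicity controlled.

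**Working it through.** **The plan's own figure.** From SAP 2.2: placebo change 6.0, SD 10.0, a 45% difference (0.45 × 6.0 = 2.7 points), 90% power, two-sided 0.05. Then n = 2 × (1.960 + 1.282)² × (10/2.7)² ≈ 288.3, so 289 per arm, as stated. The documents give no familywise error figure.

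**Upper bounds.** Two unlinked 5% routes give at most 0.05 + 0.05 = 10%, or 1 − 0.95² = 9.75% if independent. These are approached only when ADAS-Cog12 and iADRS reject almost always while ADCS-ADL and CDR-SB are null.

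**Model for the planned effect.** From the documents: 289 per arm, ADAS-Cog12 SD 10, iADRS = (80 − ADAS-Cog12) + instrumental ADL. Assumed, because the documents do not give them: SD of change 9 for instrumental ADL and 4 for basic ADL, one common correlation r from 0 to 0.7, and a drug effect on cognition only. A false claim is ADCS-ADL through the co-primary pair, or CDR-SB through the chain. With every later endpoint null as well, nothing beyond CDR-SB adds to the error, because the chain reaches it only after a false CDR-SB claim.

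**By hand at r = 0, effect 2.7.**

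- ADAS-Cog12: 2.7 / (10 × √(2/289)) = 3.25, power 0.901.
- iADRS: SD = √(100 + 81) = 13.45; 2.7 / (13.45 × √(2/289)) = 2.41, power about 0.675.
- False claim through the pair: 0.901 × 0.05 = 0.045.
- False claim through the chain: 0.675 × 0.05 = 0.034.
- Overlap: the pair and iADRS are jointly significant in about 0.025 of trials (simulated); × 0.05 = 0.001.
- Total: 0.045 + 0.034 − 0.001 ≈ 0.078.

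With an entry condition on both co-primaries, only the 0.045 remains.

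**Simulation over r = 0 to 0.7, 289 per arm, cognition-only effect.**

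| ADAS-Cog12 effect | Share of placebo decline | Error as written (r = 0.7 to r = 0) |
|---|---|---|
| 2.7 points | 45% | 4.7% to 7.8% |
| 4 points | 4/6 = 67% | 6.5% to 9.5% |
| 6 points | 6/6 = 100% | 7.9% to 9.7% |

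With the entry condition the error is at most about 5.0% in every row. Under the global null the rule as written gives about 5%, because the joint co-primary win is rare and iADRS shares its components.

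**Fewer participants.** The mITT restriction and early termination will probably leave fewer than 289 per arm, and the SAP does not say how many. At 2.7 points the error as written is 4.2% to 6.4% with 200 per arm and 4.0% to 5.2% with 150 (both sizes illustrative).

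**A second set of assumptions.** With equal-variance iADRS components and a correlation of 0.9 between total and instrumental ADL, the planned-effect range is 5.0% to 7.6%.

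**Secondary claims after a failed co-primary.** At 2.7 points iADRS has power of about 67% (r = 0) to 46% (r = 0.7). Subtracting the roughly 2.5 points in which the co-primary pair also succeeds leaves 65% to 43% of trials in which iADRS is declared although the success rule failed. The second set of assumptions gives 40% to 61%.

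**The case against.** The strongest reply is that this is an omission and not an adopted design. The endpoints are called co-primary, they come first in 6.1.3, and the strategy is described as gatekeeping. The SAP cites the protocol as reference material, says the primary objective is unchanged, and records no changes from planned analysis. On that reading the both-must-win rule still stands.

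That reply holds for study success. A reader might infer from "will each be tested at p=0.05 using the mITT analysis set" that one co-primary now suffices, or that a failed co-primary could become a successful trial. The documents do not support that, because protocol 11.3.1 is not withdrawn.

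It does not hold for the secondaries. The gatekeeping sentence limits itself to them, and the protocol never tied them to the co-primaries. For the 50 mg arm, where the protocol did state the condition, the SAP replaces it with endpoint-by-endpoint carry-over, so an unstated both-co-primaries condition cannot be presumed.

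The objection on size also stands in large part. The near-10% figures need 67% to 100% slowing of cognitive decline with no effect on any ADL item or on CDR-SB. At the planned effect and r = 0.7 the error is below 5%. The ADL SDs and all the correlations are assumptions.

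**Conclusion.** The entry condition is missing, and it matters for which claims count as confirmatory. As written, the co-primary pair and the mITT 100 mg chain together do not have strong 5% familywise control. The excess appears only under partial nulls. It reaches at most about 2.8 percentage points at the planned effect (7.8% − 5.0%), is absent at the highest correlation considered, shrinks with fewer participants, and approaches 5 points only for very large cognition-only effects.

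Two stronger readings should be avoided. One is that the 100 mg error rate is simply 10%: it is about 5% under the global null and depends on unknown correlations elsewhere. The other is that the 43% to 65% figure is a false-positive rate: iADRS has a true effect in that scenario through its ADAS-Cog12 component, so rejecting it is correct. What is wrong there is the status of the claim, which would be formal although the trial failed its own success rule.

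**What to change.** Before unblinding, make three edits to the SAP.

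1. Add to 6.1.3: *Success is declared only if both 100 mg co-primary comparisons are significant at two-sided 0.05 in favour of simufilam; the secondary chain is tested only in that case, otherwise secondary p-values are nominal.*
2. Put the same both-co-primaries condition in front of the 50 mg sentence, in line with protocol 11.3.2.
3. Correct the Type 1 error cross-reference in 4.2 from 6.1.2 to 6.1.3.

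This limits the error to 5% for the co-primary pair and the mITT 100 mg chain only. The 50 mg and ITT-mild tests branch from the same set of significant endpoints, each at 0.05, and need their own place in the hierarchy if they are to support controlled claims.

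The cost is a few lines of text and no new data. The downside is that no formal secondary claim is available if a co-primary fails.

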# 11.3.3 Other Secondary Analyses

The iADRS is a linear combination of scores from two well-established, widely accepted, therapeutically sensitive measures of AD: the ADAS-Cog and ADCS-iADL (the instrumental component of the ADCS-ADL). The iADRS has been validated and statistical properties of the composite performance have been described. All items of the ADAS-Cog12 and the ADCS-iADL will be included to generate this primary efficacy composite measurement without additional weighting.

Secondary clinical endpoint data (iADRS, NPI, MMSE, and ZBI) measured repeatedly will be analyzed by linear mixed models for repeated measurements, as described above for the primary analysis.

Plasma assays may include P-tau181 and/or P-tau217, SavaDx, neurofilament light chain, and other biomarkers. All plasma biomarker data and MRI data measured repeatedly will be analyzed by linear mixed models for repeated measurements, as described above for the primary analysis.

CSF biomarker endpoints to be analyzed currently include: 1) neurogranin, 2) neurofilament light chain, 3) total tau, 4) P-tau181 and/or P-tau217, 5) sTREM2, and 6) A $\beta_{42}$ . Additional CSF biomarkers may be measured. All CSF biomarker data, PET imaging data, and CDR-SB will be analyzed using ANCOVA models with treatment group as a factor and the baseline value of the corresponding endpoint as a covariate.

All secondary analyses will be conducted using two-sided tests at the alpha = 0.05 level of significance, with no adjustments for multiplicity.

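### SAP 6.1.3 tests up to seven 50 mg endpoints at a full 0.05 with no order or stop, and starts the mild chain at another 0.05, so the 50 mg claims, and the 50 mg and mild claims together, are not held at 5%

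*SAP*

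**What the plan says.** SAP 6.1.3 tests ADAS-Cog12 and ADCS-ADL at 100 mg, each at 0.05, in the mITT set. It then tests five secondaries at 100 mg in the order iADRS, CDR-SB, ZBI, MMSE, NPI-10, stopping at the first failure. Its explicit statement of multiplicity control covers only the 100 mg arm in mITT.

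Two further sets of tests follow.

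- **50 mg:** "Endpoints that were significant in the 100mg arm will also be tested in the 50mg arm at P = 0.05". Nothing more is said about order, stopping, alpha or a both-must-pass rule.
- **Mild:** for the endpoints that succeed at 100 mg, "the corresponding endpoints in the mild subgroup (ITT-mild analysis set) will be tested". Then: "Testing for the mild cohort will proceed in the same order as for the secondary endpoints referenced above until the first non-significant p value". Endpoints that pass before the stop are to be called significant. The co-primaries are given no place in this order.

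The protocol was narrower. Under 11.3.2, once both 100 mg co-primaries pass, "the corresponding comparisons at Week 76 for the 50 mg group versus the placebo group will be tested"; this concerns the two co-primaries only. For everything else, 11.3.3 says: "All secondary analyses will be conducted using two-sided tests at the alpha = 0.05 level of significance, with no adjustments for multiplicity".

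On status, SAP 4.2 separates two kinds of result. One is controlled: "Efficacy results will be considered statistically significant after consideration of the strategy for controlling the Type 1 error". The other is not: "Nominal p-values may be computed for other efficacy analyses". SAP 6.1.3 does not say which kind a 50 mg result on the five secondaries is. SAP 3.1.2 says multiplicity is controlled for the five secondaries without limiting that to one dose. SAP 3.2 lists 50 mg as a secondary treatment under the multiplicity-controlled estimands.

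**The concern.** Passing at 100 mg is a useful gate when nothing works. It gives no protection when 100 mg works and 50 mg does not, and that is a case strong control has to cover. The 50 mg tests open only after success at 100 mg, and from then on each has a full 5% chance of a false result with nothing limiting how many are tried. The mild chain draws a further 5% from the same gate without depending on the 50 mg results, so the same alpha is spent more than once.

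At stake are the claims that the lower dose works and that the drug works in mild disease. A reader who sees the hierarchy in 6.1.3 and the promise of control in 3.1.2 would reasonably take such results as protected.

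**Working it through.** **The plan's own figure.** SAP 2.2 assumes a placebo change of 6.0, SD 10.0 and a 45% difference, so the effect is 0.45 × 6.0 = 2.7. Then n = 2 × (1.960 + 1.282)² × 10² / 2.7² ≈ 288.3, giving 289 per arm as stated. 289 / 0.8 = 361.25 (361 stated), and 3 × 361 = 1083. This reproduces. It powers ADAS-Cog only, at 90%, so the 90% row below is the natural reference.

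**Number of 50 mg tests.** 2 co-primaries + 5 secondaries = 7.

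**Independent-test reference, 100 mg certain to pass on all seven.** 50 mg alone: 1 − 0.95⁷ = 30.2%. 50 mg plus the first mild test: 1 − 0.95⁸ = 33.7%.

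**Correlated endpoints.** The documents give no endpoint correlation and no share of mild participants. Assumptions:

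- endpoint correlation 0.3 to 0.8, and 60% mild;
- both 100 mg co-primaries form the gate, and the secondaries follow in order;
- mild is tested at 100 mg with the co-primaries first;
- no effect at 50 mg, and none in mild;
- arms are equal, so the 100 mg and 50 mg statistics on one endpoint correlate 0.5 through the shared placebo arm, and the mild 100 mg and overall 50 mg statistics correlate √0.6 / 2 = 0.39;
- each 100 mg statistic has mean 1.96 + z(power), for example 1.96 + 1.28 = 3.24 at 90%.

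A two-sided false result is |z| > 1.96 on any 50 mg test that is reached, or on the first mild test. The beneficial direction counts z > 1.96 only, with reference level 2.5%. The two-sided ranges cover a common-correlation model and one that builds iADRS from the co-primary scores, with iADL approximated by ADL (300,000 to 400,000 runs). The beneficial column uses the common-correlation model.

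| Power of each 100 mg test | 50 mg or mild, two-sided | 50 mg or mild, beneficial | 50 mg alone, two-sided |
|---|---|---|---|
| 90% | 13-20% | 9-14% | 10-18% |
| 70% | 9-11% | 8-10% | 7-10% |
| 50% | 7-8% | 6-7% | 5-6% |
| 30% | 3-5% | 3-5% | 2-4% |
| certain to pass | 18-30% | 9-15% | 14-27% |

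**Mild chain alone.** 5.0% with the gate certain, and about 3% at 90% power. If its co-primaries were instead tested outside the listed order, it would be 8-14% with the gate certain (correlation 0.9 down to 0).

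**Protocol 11.3.2 alone, gate certain.** The two 50 mg co-primary tests give 8-10% if either can be claimed, and 0.5-2.2% if both must pass.

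**Adding an order and stop at 50 mg only, gate certain.** 50 mg falls to 5.0%, but 50 mg or mild together is still about 9%.

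**Sensitivity.** ITT-mild is defined on all randomized participants and so is not nested in mITT. Letting mITT be 50-100% of ITT and mild 40-80% moves the 90% row by less than 1 point.

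**The case against.** Five points can be made for the plan.

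1. **The mild chain is ordered.** A reader might infer that mild claims by themselves exceed 5%. The documents do not support that: the chain has an order and a stop, and with the co-primaries first it never exceeds 5%. Only the joint 50 mg and mild family does. This objection stands.
2. **The 50 mg secondaries may be nominal.** The control statement in 6.1.3 is limited to 100 mg in mITT, and the 50 mg sentence, unlike the other two chains, never says that a pass will be called significant. A reader might infer that these five are confirmatory; SAP 3.1.2 and 3.2 lean that way but do not settle it. If they are nominal, the seven-test percentages do not apply to them. The two 50 mg co-primaries are a gated key secondary under protocol 11.3.2 in any case.
3. **The SAP is not simply looser than the protocol.** Protocol 11.3.3 already left the other secondaries unadjusted and ungated, so for those the SAP adds a gate. That is true, but the gate does not limit error among the 50 mg tests once it is open.
4. **Two-sided counts include results in the harmful direction, and the all-certain case is a corner.** Both are fair. The beneficial-direction rates at 90% power, 9-14% against 2.5%, are the sober measure, and they remain well above the reference.
5. **The dose for the mild tests can be inferred.** A reader might infer that it is missing. SAP 3.2 sets 100 mg against placebo as the main comparison and then changes only the population, and 6.1.3 refers back to the 100 mg endpoints. It needs confirming, not inventing. The place of the co-primaries in the mild order is truly unstated.

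**Conclusion.** The concern holds for the 50 mg family and for 50 mg and mild taken together. Followed as written, the rule gives false-positive rates above 5% whenever 100 mg works reasonably well and 50 mg does not. The size depends on the correlation, mild share and power assumed above; at 30% power per test the two-sided excess over 5% largely disappears.

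A reader might also infer that the 100 mg results are compromised. They are not: they stay at 5% provided both co-primaries must pass before iADRS is tested. Protocol 11.3.1 implies this by requiring both for study success, but SAP 6.1.3 does not state it. If nothing works at any dose, that same gate keeps false 50 mg or mild results to 0.5-2.2%. This should be fixed, but it does not undermine the primary analysis.

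**What to change.** Before unblinding, rewrite SAP 6.1.3 so that the 50 mg and mild tests sit in one scheme held at two-sided 0.05, and label any test left outside it nominal. One scheme that works is a single fixed sequence with a stop: 100 mg co-primaries, 100 mg secondaries, 50 mg co-primaries, 50 mg secondaries, then mild with its co-primaries first. Its largest simulated error over 125 mixed-null configurations was 5.09%, which is 5% plus simulation noise. Another order, or an alpha split between branches that each have an order and a stop, is equally acceptable if it holds 5%; the choice is the sponsor's. An order and stop at 50 mg alone is not enough.

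In the same edit:

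- state that both 100 mg co-primaries must pass before iADRS;
- state whether 50 mg on the five secondaries is confirmatory or nominal;
- give the co-primaries a place in the mild order;
- confirm that the mild tests are the 100 mg comparison;
- correct the SAP 4.2 cross-reference for Type 1 error from 6.1.2, which covers covariates, to 6.1.3.

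The change is wording only, but later tests are reached less often. With each 100 mg test at 90% power, the current rule reaches the 50 mg and mild tests in 82-86% of trials. The single sequence reaches 50 mg in 59-78%. It reaches mild in under 0.5% if 50 mg has no effect, 7-25% if each 50 mg test has 50% power, and 45-65% at 90%. With a three-way alpha split, a test with 90% power at 0.05 has 80% at 0.05/3. If the data are already unblinded, report the 50 mg and mild results as nominal.
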